8.2.1 Inclusion Criteria

A patient's eye must meet **all** of the following criteria to be eligible for participation in the study.

1. Eye treated with XEN 45 Gel Stent for open angle glaucoma as a standalone procedure or in combination with phacoemulsification
2. XEN 45 Gel Stent was implanted between 1 January 2014 and 1 October 2015

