1.6. Study Design

This is a retrospective, non-interventional, observational, multi-centre, chart review study conducted in patients who underwent placement of the XEN 45 Gel Stent as a standalone procedure or in combination with phacoemulsification from 1 January 2014 to 1 October 2015.

For each eligible eye, all retrospective data available from baseline (i.e. day when decision was made to implant XEN 45 Gel Stent) until Last Visit (i.e. date of the last follow-up visit available prior to 1 October 2018 or date on which the patient had a SSI for glaucoma, whichever occurs first) are extracted from existing medical records into the electronic CRF (eCRF) in Dacima.

If both eyes from the same patient meet eligibility criteria, each eye is included in the study database with a unique identifier and eyes are paired in the electronic data capture system (EDC). See section 4 for how bilateral eyes included in the study are handled in the analyses.

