3.4. Missing Data

The eCRF is designed to ensure that no questions are left unanswered. If 'unknown' is selected, this will be included as such in the results and tabulated for all variables. Central tendencies will not be measured for continuous unknown data, only counts and percentages will be recorded.

In some cases, imputation of unknown variables may be conducted if the variable is to be used in calculations for another variable or analysis. For example, the eCRF allows some dates to be incomplete (i.e. day is unknown) if it is not available in the medical chart. This may impact accurate calculation of durations, resulting in an imputation needing to be made. If the day is missing, the date will be imputed as the 15th of the month, except in cases where this would lead to a negative duration, in which case the 1st or last day of the month will be used (whichever addresses the negative duration). No imputation will be made for missing month/year; these are classified as date unknown within the eCRF. All imputed values will be documented and presented as footnotes in the result tables.

4. Planned Analyses

The analyses detailed below will be performed to meet the project objectives. There will be two analysis populations specified for the analyses to be conducted:

- The **Effectiveness Population** consists of all eligible study eyes in the population except in instances when a patient has contributed both eligible eyes in the study, then only the eye that received the Xen-45 implant first will be selected; this eye will be presented in tables as the 'primary eye'. All results tables in the Effectiveness Population will include stratified results presenting data for the primary eye, as well as data on all included patient eyes (even if both eyes from a single patient are included).
- The **Safety Population** consists of all eligible study eyes in the population.

All results tables will be stratified by Xen-45 implant only, implant plus phacoemulsification, and total population. Sensitivity analyses will be conducted to assess study results in the 'second eye' (i.e. not the primary eye as described above), for patients where both eyes were included. The sensitivity analyses will focus on the tables conducted using the Effectiveness Population.

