4.1. Time Windows for Follow-up Period

For IOP and number of IOP-lowering medications only, data from the latest clinic visit recorded within the following time windows will be used in the analysis:

- Month 12: data between Month 9 and Month 15 after XEN 45 Gel Stent implantation
- Month 24: data between Month 21 and Month 27 after XEN 45 Gel Stent implantation
- Month 36: data between Month 33 and Month 39 after XEN 45 Gel Stent implantation
- Month 48: data between Month 45 and Month 51 after XEN 45 Gel Stent implantation
- >Month 51 after XEN 45 Gel Stent implantation

Unless otherwise specified, all other retrospective data (See Section 1.8) collected from baseline until the last visit will be categorised into the following groups for the follow-up period analyses, based on latest available data within the time window:

- ≤ 12 months: data ≤ 12 months after XEN 45 Gel Stent implantation
- > 12 to ≤ 24 months: data > 12 to ≤ 24 months after XEN 45 Gel Stent implantation
- > 24 to ≤ 36 months: data > 24 to ≤ 36 months after XEN 45 Gel Stent implantation
- > 36 to ≤ 48 months: data > 36 to ≤ 48 months after XEN 45 Gel Stent implantation
- >48 months: data from >48 months after XEN 45 Gel Stent implantation to end of study period

Needling procedures will be summarised descriptively within the following time-windows:

- < 3 months: data < 3 months after XEN 45 Gel Stent implantation
- > 6 to ≤ 12 months: data > 6 to ≤ 12 months after XEN 45 Gel Stent implantation
- > 12 to ≤ 24 months: data > 12 to ≤ 24 months after XEN 45 Gel Stent implantation
- > 24 to ≤ 36 months: data > 24 to ≤ 36 months after XEN 45 Gel Stent implantation
- > 36 to ≤ 48 months: data > 36 to ≤ 48 months after XEN 45 Gel Stent implantation
- > 48 months: data > 48 months after XEN 45 Gel Stent implantation

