These will be compared to baseline and will be summarised descriptively at months 12, 24, 36 and 48 after XEN 45 Gel Stent implantation in eyes from the Effectiveness Population. Analyses will only include those with available data at each of the time points of interest and those who were not treated with Diamox on the day when decision was taken to implant XEN 45 Gel Stent.

A paired t-test will be applied for statistical analysis in comparing the difference between post baseline to baseline values. The assumptions of the test are as follows:

- No significant outliers in the differences between time points (which can be tested by a scatter plot of the data)
- The distribution of the differences in the dependent variable between the two time points should approximately follow a normal distribution (which can be tested through the Shapiro-Wilk test)
- The dependent variable is measured on a continuous scale

If the assumptions of the t-test are heavily violated then the non-parametric analogue (Wilcoxon Signed-Rank test) should be used to test the difference between time points.

4.4.1. Success over the long term of following implantation of the XEN 45 Gel Stent

Number and proportion of eyes achieving a 20% reduction in IOP from medicated baseline, and number and proportion of eyes with an IOP between 6 and 18 mmHg, IOP between 6 and 17 mmHg, ..., down to IOP between 6 and 12 mmHg will be described by the time-windows described in Section 4.1 in eyes from the Effectiveness Population that did not undergo SSI for glaucoma, and were not treated with Diamox on the day when decision was taken to implant XEN 45 Gel Stent.

The number and proportion of eyes achieving qualified or complete success at each time point of interest (i.e. 12, 24, 36, 48 and >51 months) after XEN 45 Gel Stent implantation will be summarised descriptively. Analyses will be conducted in the Effectiveness Population.

The time from XEN 45 Gel Stent implantation to SSI for glaucoma will be described using Kaplan Meier curves.

4.5. Safety over the long term following implantation of the XEN 45 Gel Stent

Surgical complications and post-operative AESIs will be summarised descriptively using frequencies and percentages.

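### SAP 4.4.1 sets no denominator for success at Month 48 and beyond Month 51, for eyes that cannot reach those windows by 1 October 2018 or whose extraction stopped at SSI

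*SAP*

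**What the plan says.** SAP 4.4.1 summarises qualified or "complete success at each time point of interest (i.e. 12, 24, 36, 48 and >51 months", and the only statement about who is counted is "Analyses will be conducted in the Effectiveness Population". SAP section 4 defines that population: it "consists of all eligible study eyes in the population except in instances when a patient has contributed both eligible eyes in the study", in which case the first-implanted eye is used. Length of follow-up plays no part in the definition.

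Eligibility and cut-off are fixed by date. Protocol 8.2.1 requires that "XEN 45 Gel Stent was implanted between 1 January 2014 and 1 October 2015". SAP 1.6 ends extraction at the "date of the last follow-up visit available prior to 1 October 2018" or at the SSI date if that is earlier. SAP 4.1 gives the late windows as "Month 48: data between Month 45 and Month 51 after XEN 45 Gel Stent implantation" and ">Month 51 after XEN 45 Gel Stent implantation".

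The analyses of change in IOP and medications are treated differently. SAP 4.4 says of them: "Analyses will only include those with available data at each of the time points of interest". Protocol 14.2.5.1 likewise limits the 4-year change to eyes with at least 4 years of follow-up, while Protocol 14.2.5.2 puts 4-year success in the Analysis Population without that condition.

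**The concern.** Success at 4 years is a named outcome in both documents, and long-term data are the stated reason for the study. Two groups of eyes make the late proportions depend on a rule that the SAP does not give.

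The first group is eyes implanted too late to have a visit in the window. If they stay in the denominator they can never be counted as successes, and the proportion falls for a reason unrelated to the device. The second group is eyes with an SSI. They are failures by the definition in SAP 1.4, but extraction stops at the SSI, so they have no later IOP. If only eyes with data are counted, these failures disappear and the proportion rises.

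The stated population and the nearest available-data rule therefore err in opposite directions. Without a written rule, the choice would be made after the data are seen, and proportions at Month 36, Month 48 and beyond Month 51 would not be comparable.

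**Working it through.** The documents give no figure for the number of eyes expected in the late windows, so there is no plan figure to reproduce. The confidence interval in SAP section 2 concerns mean IOP change and does not bear on this point.

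**Inputs from the documents.** Implants from 1 January 2014 to 1 October 2015 (Protocol 8.2.1). Visits before 1 October 2018 (SAP 1.6). Month 48 window opening at Month 45, and last window opening after Month 51 (SAP 4.1). First screening log limited to 2014 implants, with three-month extensions only if the target is not met (Protocol 9.2). 150 eyes (SAP section 2).

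**Assumptions.** Implants spread evenly by day; true success of 50% among eyes that can reach the window. The documents give neither.

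**Step 1: latest implant date for each window.**
- 1 October 2018 minus 33 months = 1 January 2016, after the last eligible implant. Every eye can reach the Month 36 window, and so the earlier ones.
- 1 October 2018 minus 45 months = 1 January 2015. Eyes implanted on or after that date cannot reach the Month 48 window. An implant on 31 December 2014 reaches Month 45 on 30 September 2018.
- 1 October 2018 minus 51 months = 1 July 2014. Eyes implanted on or after that date cannot pass Month 51.

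A day either way at these boundaries makes no practical difference.

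**Step 2: share of eyes out of reach, and the result if they stay in the denominator.** Reachable share r = implant days early enough / all implant days. Reported proportion = 0.50 × r.

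| Screening ends | Days | Reach Month 45 | Out of reach | 50% reads as | Pass Month 51 | Out of reach | 50% reads as |
|---|---|---|---|---|---|---|---|
| 31 Dec 2014 | 365 | 365 | 0% | 50% | 181 | 50% | 25% |
| 31 Mar 2015 | 455 | 365 | 20% | 40% | 181 | 60% | 20% |
| 1 Oct 2015 | 639 | 365 | 43% | 29% | 181 | 72% | 14% |

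Of 150 eyes, 150, 120 and 86 could reach Month 45, and 74, 60 and 42 could pass Month 51. These counts are before loss to follow-up and before reduction to one eye per patient. With true success of 40% to 60%, accrual to 1 October 2015 gives 23% to 34% at Month 48 and 11% to 17% beyond Month 51. With 2014 implants only, the figures are 40% to 60% and 20% to 30%.

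**Step 3: the available-data rule instead.** Let s be the share of reachable eyes with an SSI before the window, and let 50% of the rest succeed. The correct proportion is 0.50 × (1 − s). Counting only eyes with data gives 50% whatever s is. For an assumed s of 10% to 30%, the correct figure is 45% to 35%, so success is overstated by 5 to 15 percentage points. This does not depend on accrual.

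**Step 4: truncated windows.** Eyes implanted from 1 July to 31 December 2014 can enter the Month 48 window but cannot complete it. Those implanted on or after 1 October 2014 (1 October 2018 minus 48 months) do not complete 48 months before the cut-off.

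**The case against.** Naming an analysis population does not put every member into every denominator. SAP 4.4.1 is a subsection of 4.4, so the available-data sentence may be meant to carry down. A third reading also exists. The threshold analysis in 4.4.1 removes eyes with an SSI and the success paragraph does not, which suggests that SSI eyes stay in as failures. SAP 3.4 and section 4 tabulate unknown responses, so eyes without data could be shown as unknown. That would be close to the right analysis. SSI is also reported by Kaplan-Meier and by time window, so its loss from the success table would be visible. Finally, the analysis is descriptive, and the window most exposed, beyond Month 51, is not among the named 3- and 4-year outcomes.

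Much of this stands. A reader might infer that the plan counts administratively censored eyes as failures; no passage says so. A reader might also infer that every reading of the text is biased; the third reading is not. And a reader might take 43% unreachable, with 50% reported as 29%, as the expected Month 48 effect. That needs screening to run to 1 October 2015, whereas Protocol 9.2 starts with 2014 implants, all of which can reach Month 45.

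The point survives because the third reading has to be assembled from inference. SAP 4.4.1 restates the Diamox exclusion for its threshold analysis, so restrictions appear to be set analysis by analysis, and the success paragraph has none. The available-data sentence in 4.4 belongs to Months 12 to 48 and does not mention the window beyond Month 51. The rule on unknowns does not say whether they enter the percentage denominator, and does not clearly cover an eye with no visit in a window.

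**Conclusion.** The concern holds as a missing denominator rule with a material effect on the late success proportions. It is not a finding that the plan codes unreachable eyes as failures.

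- **Beyond Month 51:** if the whole population is the denominator, dilution occurs even with 2014 implants only, where about half of the eyes cannot reach the window. With accrual to 1 October 2015 it is about 72%.
- **Month 48:** no dilution with 2014 implants only, about 20% of eyes out of reach with one extension, and about 43% with accrual to 1 October 2015. One small qualification: Protocol 9.2 admits a patient's second eye whatever its implantation date, so a few 2015 eyes could enter the all-eyes rows even without an extension.
- **Available-data rule:** eyes with a prior SSI drop out and success is overstated, by an amount that depends on the SSI rate.

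The shares rest on uniform accrual and the reported proportions on an assumed 50% true success; the boundary dates rest on the documents alone. No hypothesis test on success is planned, so no error rate or power is affected. The change should be made before analysis, but it does not threaten the primary objective.

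**What to change.** In SAP 4.4.1, state for each time point:

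1. The denominator is eyes implanted early enough to reach the lower bound of the window by 1 October 2018: before 1 January 2015 for Month 48 and before 1 July 2014 for the window beyond Month 51. Decide this from the implant date alone, so that late-implanted eyes are left out whether or not they had an SSI.
2. Within that denominator, eyes with an SSI or clinical hypotony before or in the window count as failures, even with no IOP in the window.
3. Reachable eyes with no data and no SSI appear in a separate not-assessable row. Give the proportion both with and without them in the denominator.
4. A note says that eyes implanted from July to December 2014 have a truncated Month 48 window, so some not-assessable eyes there reflect the cut-off and not loss to follow-up.

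The cost is SAP wording and one derived flag from the implant and SSI dates already collected. Both boundaries fall on the first of a month, so the mid-month imputation of missing days in SAP 3.4 does not change the flag. The Month 48 denominator shrinks if 2015 implants are included, and the denominator beyond Month 51 shrinks in any case. Precision at those points will be lower and should be reported as such.

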4.6. Secondary surgical intervention

The median time for a patient in the Safety Population to have an SSI will be described by Kaplan-Meier curves. A summary of patients with SSI will be recorded by the time windows described in Section 4.1.

7. References

1. Glaucoma Panel. *Preferred practice pattern for primary open-angle glaucoma*. San Francisco 2006.
